**b) Data Safety Monitoring Board (DSMB)**

Safety oversight will be conducted by a DSMB that is an independent group of experts that monitors subject safety. The DSMB members will be separate and independent of study personnel participating in this trial and should not have scientific, financial, or other conflict of interest related to the study. The DSMB will consist of three members with appropriate expertise to contribute to the interpretation of the data from this trial: malaria in pregnancy, maternal-fetal medicine and biostatistics.

The DSMB will review and approve the study protocol and safety plan prior to initiation of the trial. It will be convened when 50% of the planned subjects have been enrolled for a review of interim data. The PI will review safety data weekly and report any serious adverse events to the DSMB and IRB and to NIH/NICHD. The DSMB and NIH will receive quarterly adverse event reports and the interim report will include the following information: recruitment, withdrawals, loss to follow up, adverse events, and medication tolerance. The DSMB will also review efficacy and safety data after all subjects have been enrolled in a final closeout meeting, held at the end of the study. As an outcome of each review/meeting, the DSMB will make a recommendation as to the advisability of proceeding with study and to continue, modify, or terminate the study.

**X. SPECIMEN COLLECTION AND PROCESSING**

All samples will be collected under practices outlined in SOPs and they will be labeled with unique study ID, visit number and date. Malaria testing: Blood will be collected by fingerstick for thick smear microscopy and dried blood spots (DBS) will be collected on filter paper for PCR testing later. Blood will also be collected by venipuncture for CBC, differential and RPR testing, as indicated. RPR will be performed on women with a prior positive treponemal test during antenatal care if not performed previously. Microscopy, CBC, and syphilis testing will be performed at the facility laboratory but same day results cannot be guaranteed. Subjects will be called by telephone with positive results that return after they have left the facility along with

specific follow up instructions. Filter paper with DBS will be stored in the freezer (-20 degrees C) with regular transportation to the University of Buea for long term storage and PCR testing.

Placental biopsies will be collected on as many women as possible at the time of facility delivery. Slides will be created with impression smears and placental blood will be collected on filter paper for PCR testing.

STI testing: Vaginal swabs will be collected at enrollment for storage and at the 35-42 week or delivery or post-delivery visit (whichever comes first) for GC/CT NAAT testing as well as an anogenital swab for GBS NAAT testing per SOPs. pH indicator sticks will be used to collect a sample from the lateral vaginal wall. Slides will be prepared from a vaginal swab at the late pregnancy visit.

Vaginal Swab specimens for Future Testing: Vaginal swabs will be stored in transport media using buffer in a -20 freezer until they can be transported to the UAB STI laboratory for later STI testing. Participants will be asked to sign a consent specifically for their agreement to have these samples stored and shipped to UAB for future analysis. For those who do not consent, the samples will be destroyed at the end of the study. Before specimens leave the clinic, they will be assigned a unique code. Specimens stored for future research will be shipped to the UAB STI Research Laboratory at the University of Alabama at Birmingham (UAB) ([name] [name] Lab, [name] Mycoplasma/Ureaplasma Laboratory) where they will be stored according to GCLP by the Laboratory Managers.

## **XI. SAMPLE SIZE CONSIDERATIONS**

AIM 1: To test the hypothesis that the addition of AZ to standard preventive therapy in pregnant women with HIV will be associated with a lower proportion of women with peripheral parasitemia detected by microscopy or PCR at delivery, we assumed a 30% prevalence of parasitemia in the TMPS arm based on prior studies and 15% prevalence in the TMPS/AZ arm. A sample size of 134 pregnant women per arm has 80% power at a two-sided significance level of 0.05 using a chi-square.

We will plan for 15% loss to follow up (LFU) and will recruit 154 women per arm (308 women total).

AIM 2: Based on the sample size of 308 evaluable participants at the time of delivery and an expected prevalence of 30% for one or more STIs (CT 20%, GC 5%, syphilis 5%) there will be >80% power at a two-sided significance level of 0.05 to detect a 50% lower STI prevalence in the intervention arm.

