### **Curable bacterial STIs are common in pregnant women with HIV in Africa and an important cause of maternal and neonatal morbidity.**

Accumulating evidence supports infection as a major cause of spontaneous preterm labor, particularly when it occurs before 30 weeks gestation.(25) The underlying pathogenesis is under study, but proinflammatory cytokines IL-6, TNF, IL-1, metalloproteinase-9 and alterations in the maternal microbiome contribute to uterine activation.(26-30) HIV prevalence in pregnancy is elevated in Africa (10% in urban Cameroon) and antenatal screening suggests a high rate of STIs in women with HIV.(31, 32) In one study, 38% of pregnant women with HIV had CT (compared to 7% in HIV-uninfected), 10% had GC (compared to 3%) and 36% had syphilis (compared to 11%). Up to 90% of pregnant women with early syphilis transmit *Treponema pallidum* to the fetus which can lead to stillbirth, neonatal deaths, congenital syphilis and low birth weight. There are an estimated 200,000 adverse pregnancy outcomes attributable to syphilis in sub-Saharan Africa each year and adequate prevention could reduce stillbirths by 80% worldwide.(33, 34) Although GC/CT infections are generally confined to the lower genital tract, GC acquisition in pregnancy has been associated with preterm birth (aOR 2.1, 95% CI 1.02-3.97) and CT infection with low birthweight (aOR 2.07, 95% CI 1.01-4.24).(35, 36)

**More effective prevention tools for malaria and sexually transmitted infections are needed for the high-risk population of HIV-infected pregnant women.**

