## **XII. DATA ANALYSIS AND MANAGEMENT**

Data management and analysis will be led by the University of Alabama at Birmingham under the supervision of the study PI ([name]).

The primary analysis will be by intention to treat for women who are randomized and receive at least 1 dose of study medication.

The “per protocol” analysis will be performed on women who came to at least one follow up visit following the enrollment visit, reported excellent (>90%) medication adherence, and had outcomes captured (ie – not lost to follow up).

**Statistical Analysis:** Descriptive statistics will be used to compare the study participants between each arm and the primary analysis will be intention-to-treat for the primary outcome of proportion of women with parasitemia. The analysis plan for categorical outcomes is chi-square, Fisher’s exact tests as needed for small sample sizes and we plan to use t-test and Wilcoxon Rank-Sum tests for continuous outcomes. Women will be considered lost to follow up if they do not have a study visit after 35 weeks or at delivery for outcome ascertainment.

For the secondary outcomes, the significance of differences in proportion will be explored using the Pearson’s  $\chi^2$  test or Fisher’s exact test. Multivariable regression modeling will be used to evaluate baseline factors associated with parasitemia if there is imbalance between the arms despite randomization. Potential covariates include age, parity, educational level, monthly income, marital status, history of negative birth outcomes, CD4 count, ART adherence, bed net usage, malaria treatment received and number of study visits. All analyses will be performed in SAS v 9.3.

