### XIII. STUDY TIMETABLE

	2017	2018	2019	2020
IRB Approval	X			
Hire Study Staff	X			
Training	X			
Enrollment		X	X	
Subject Follow Up		X	X	
Data Processing		X	X	
Data Analysis				X

- a) IRB Approval – see ethical considerations in subsequent section (Section XIV).
- b) Study Staff – One study nurse and one data manager will be hired at each facility and the current CHI-UAB Coordinator will assume the duties of study coordination at both sites. The study PI will be onsite several times a year for 1-2 months at a time during the study period. She will also be on site during training, study initiation and enrollment.
- c) Training – Before the trial begins, study nurses, coordinators, physician co-investigators and laboratory staff will undergo training on study procedures and data collection, including standardized testing methods for malaria and sexually transmitted infections and how to perform a surface examination for congenital anomalies at birth and collect placental biopsies.
- d) Enrollment and Follow Up – In 2014, Mboppi Hospital in Douala had more than 15,000 antenatal care visits and 4000 deliveries. Approximately 400 new pregnant patients are seen each month in clinic and approximately 24 women are HIV-infected (seroprevalence 5.9%). At the Baptist Hospital in Mutengene (BHM), the HIV seroprevalence is 10.2%, and there are 10 new HIV-infected women seen each month in clinic. Approximately 20% of women present for ANC care during their 1st trimester and 75% during the second trimester. Pregnant women routinely have 4 prenatal visits and clinic attendance rates are high with 80% facility delivery rates.

We plan to enroll approximately 18 women each month (12 in Douala, 6 in Mutengene) over an 18 month enrollment period to reach the 308 women needed. This will allow us to have 268 women with evaluable outcomes according to the power calculation stated above (this assumes 15% loss to follow up but we will strive for >95% subject retention).

- e) Data Processing and Analysis – After a three-month period for completion for data entry for the trial, the dataset will be locked and available for analysis. Approximately six months will be required to complete the final report and submit it for publication. Group meetings will be held to determine which manuscripts will be written and the appropriate team members for submitted abstracts and publications.

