# Outcome event: peripheral parasitemia			
# Placebo group event rate: 30%			
# Experimental group event rate: 15%			
# 15% loss to follow up			
# Type 1 error 5% (2-sided)			
# Power 80%			

Registered at Clinical Trials Website ([clinicaltrials.gov](https://clinicaltrials.gov)): NCT03431168

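### At the planned 15% loss, 308 enrolled leaves about 262 evaluable women, not the 268 in Section XIII or the 308 used for Aim 2

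*Combined protocol and SAP*

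**What the plan says.** Section XI sizes the trial on Aim 1: parasitemia of 30% in the control arm against 15% with azithromycin, two-sided 5% level, chi-square test, 80% power, 134 women per arm. It continues: "We will plan for 15% loss to follow up (LFU) and will recruit 154 women per arm (308 women total").

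Section XIII, item d, carries the 308 forward: "This will allow us to have 268 women with evaluable outcomes according to the power calculation stated above", and adds in brackets that "this assumes 15% loss to follow up but we will strive for >95% subject retention". Appendix A lists "15% loss to follow up" among the design assumptions, beside 308 subjects and 80% power.

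For Aim 2 (the gonorrhea, chlamydia and syphilis composite, also a primary outcome), Section XI claims more than 80% power to detect a halving from 30%. The stated basis is: "Based on the sample size of 308 evaluable participants at the time of delivery".

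Section XII defines women as "lost to follow up if they do not have a study visit after 35 weeks or at delivery for outcome ascertainment".

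**The concern.** Three figures in the plan, 308 enrolled, 268 evaluable and 15% loss, cannot all hold. Separately, 308 is the number recruited in the Aim 1 paragraph and the number evaluable in the Aim 2 paragraph just below it.

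Two things depend on this. One is whether the power claims for two primary outcomes still stand on the number of women the plan itself expects to have. The other is the benchmark for retention, since the interim report to the DSMB covers recruitment and loss to follow-up. A trial that lost exactly its planned 15% would look 6 women short of 268, and 46 short of the 308 assumed for Aim 2.

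**Working it through.** **Inputs.** From Section XI: p1 = 0.30, p2 = 0.15 (the same pair for Aim 1 and for a halved Aim 2 prevalence), two-sided alpha 0.05, power 0.80, 134 per arm, 15% loss, 154 per arm recruited. From Section XIII: 268 evaluable. From Appendix A: 1:1 allocation. I assume equal loss in the two arms.

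**Step 1. Reproduce 134.** With d = 0.15 and mean proportion 0.225, the pooled-variance formula is

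n = [1.960 × √(2 × 0.225 × 0.775) + 0.842 × √(0.30 × 0.70 + 0.15 × 0.85)]² / 0.15²
= (1.960 × 0.5906 + 0.842 × 0.5809)² / 0.0225 = 120.5, so 121 per arm.

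The continuity-corrected version is

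(n/4) × [1 + √(1 + 4/(n × d))]² = (120.5/4) × [1 + √(1 + 4/(120.5 × 0.15))]² = 133.5, so 134 per arm.

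The plan's 134 therefore matches the corrected formula, not the uncorrected one.

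**Step 2. Reproduce 154 and 308.** 134 × 1.15 = 154.1 and 268 × 1.15 = 308.2. Both match, so the loss was multiplied on. To keep 134 after 15% loss, the calculation is 134 / 0.85 = 157.6, that is 158 per arm and 316 in total, 8 more than planned.

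**Step 3. What 308 leaves.** 308 × 0.85 = 261.8, about 262 (130.9, about 131 per arm). Conversely, 1 − 268/308 = 13.0% loss. The 95% retention that the sponsor hopes for does not give 268 either: 308 × 0.95 = 292.6.

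**Step 4. Does the loss apply to Aim 2?** Section III places the Aim 2 outcome in late pregnancy or at delivery. Section X takes the swabs at the 35–42 week, delivery or post-delivery visit, whichever comes first. Section XII counts a woman as lost when she has no outcome visit in late pregnancy or at delivery. A woman lost in that sense has no Aim 2 result. I count a woman sampled only at the postpartum visit as retained. The evaluable number for Aim 2 is then also about 262.

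**Step 5. Power for 30% versus 15%.** Uncorrected:

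power = Φ[(0.15 × √n − 1.960 × 0.5906) / 0.5809].

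For the corrected basis, replace n by n × [1 − 1/(n × 0.15)]², which inverts the correction in Step 1. At n = 131 that is 118.0.

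| Evaluable per arm | Situation | Uncorrected | Continuity-corrected |
|---|---|---|---|
| 154 | no loss (Aim 2 as written) | 88.7% | 85.8% |
| 134 | the stated 268 | 84.0% | 80.2% |
| 131 | 308 with 15% loss | 83.2% | 79.2% |

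Full binomial enumeration at 131 per arm agrees: 83.7% for the uncorrected chi-square, 79.6% with the continuity correction, and about 80.1% for Fisher's exact test.

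**Step 6. Margin.** Uncorrected power stays at 80% down to 121 per arm, that is up to 1 − 242/308 = 21.4% loss. On the corrected basis, 134 per arm is needed, so the margin ends at 13.0% loss, just under the planned 15%.

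**The case against.** The strongest reply is that nothing turns on this. Six women is 2.2% of 268. No design, test or conduct decision changes, and the Aim 2 claim is only that power exceeds 80%, which holds at 131 per arm with a plain chi-square. That stands, and it makes the point minor. It does not make the stated figures right.

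It could also be said that an intention-to-treat analysis keeps all 308 women. But Section XII describes no imputation for missing outcomes, and Section XIII itself separates enrolled from evaluable women.

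A reader might be tempted by three stronger inferences. The documents support none of them.

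- **That the trial is underpowered.** The only figure clearly under target is the continuity-corrected one, and it is under by about one percentage point.
- **That one of the two power figures is the only right one.** The stated 134 points to the corrected formula for planning. Section XII names chi-square, with Fisher's exact test where samples are small, and does not say whether a correction will be applied. Its mention of Pearson's test concerns the secondary outcomes, so it does not settle the matter for two primary outcomes. Hence both figures are reported here.
- **That Appendix A is wrong to give 80% power.** That entry sits among the assumptions, with the event rates and type 1 error. It is the target from which the sample size was derived, not a claim about power at 262.

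**Conclusion.** The point holds as an arithmetic and consistency error of minor size. At the plan's own 15% loss, 308 enrolled gives about 262 evaluable women for both aims. The 268 in Section XIII is 6 too many, and the 308 in the Aim 2 statement is 46 too many.

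Like for like with the formula that produced 134, power for 30% versus 15% falls from 80.2% to 79.2%. With an uncorrected chi-square it falls from 84.0% to 83.2%. For Aim 2, moving from 154 to 131 per arm takes power from 88.7% to 83.2% uncorrected, so the claim of more than 80% holds, or from 85.8% to 79.2% corrected, where it is borderline.

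This rests on the stated event rates, equal loss in the two arms, and Section XII's definition of loss applying to both outcomes. The loss and evaluable counts are certain. The power figures depend on which formula the sponsor adopts.

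**What to change.** Keep 308 enrolled and make these wording changes:

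- **Section XIII, item d:** replace 268 with about 262 evaluable women (131 per arm) at 15% loss.
- **Section XI, Aim 2:** replace 308 evaluable with about 262.
- **Section XI, Aims 1 and 2:** state power for 30% versus 15% at 131 per arm on one named formula. That is about 79% on the continuity-corrected formula behind 134, or about 83% with an uncorrected chi-square. Name the formula behind 134 in the same place. Otherwise 80% at 134 beside 83% at 131 would look contradictory.
- **Appendix A:** no change. The 80% remains the design target.

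The cost is a few lines in two sections, with no more participants and no change to design or conduct. If the sponsor prefers to hold 134 evaluable per arm, that takes 316 enrolled, 8 more women, but the size of the effect does not require it.

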#### a) Primary Outcomes

**Aim 1** Proportion of women with *Plasmodium falciparum* peripheral parasitemia by microscopy or PCR.

**Aim 2** Prevalence of a composite STI measure (GC, CT, syphilis infections) will be measured in both groups in late pregnancy (>35 weeks gestation) or at delivery and compared between the two groups.

[figure not shown]
**Aim 3** a) Mean infant birthweight; b) Proportion with adverse birth outcomes, including low infant birthweight (<2500 gm), miscarriage (<28 weeks), preterm delivery (<37 weeks), small for gestational age (SGA), stillbirth (>28 weeks), congenital anomaly at birth, early neonatal mortality (within 7 days); and c) maternal adherence to and tolerance of the prophylactic regimen (vomiting, rash/allergic reactions, dizziness, weakness).

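### Aim 2 power takes the no-overlap ceiling (30%) as the expected composite STI prevalence and counts all 308 recruited women as evaluable; at 268 evaluable the margin over 80% largely disappears

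*Combined protocol and SAP*

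**What the plan says.** The Aim 2 primary outcome (Section III.a) is "Prevalence of a composite STI measure (GC, CT, syphilis infections"), measured in late pregnancy or at delivery and compared between arms. Section XI, Aim 2, holds its only power statement, which has three parts:

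- Sample: "Based on the sample size of 308 evaluable participants at the time of delivery".
- Control rate: "an expected prevalence of 30% for one or more STIs (CT 20%, GC 5%, syphilis 5"%).
- Claim: "there will be >80% power at a two-sided significance level of 0.05", "to detect a 50% lower STI prevalence in the intervention arm".

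The Aim 1 text just above it plans for 15% loss to follow-up and recruits 154 per arm, 308 in total. Section XIII(d) says of the same 308: "This will allow us to have 268 women with evaluable outcomes". The plan does not say how the 30% was obtained and does not mention co-infection.

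**The concern.** Two inputs to one power sentence are each set at their most favourable value.

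First, the prevalence of at least one infection equals the sum of the component prevalences only when the infections never occur together. The plan presents this ceiling as the expected value.

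Second, 308 women can be evaluable only if nobody is lost, yet the same section budgets 15% loss. Section XII counts a woman as lost if she has no study visit after 35 weeks or at delivery. The Aim 2 specimens are due in that same window, so the loss applies to Aim 2 as much as to Aim 1.

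At stake is how an Aim 2 result would be read. A null finding on a primary outcome would carry a stated power that the plan's own evaluable number may not support.

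**Working it through.** **Inputs.** Components CT 20%, GC 5%, syphilis 5%; 50% lower composite; two-sided 0.05; 308 evaluable (all Section XI). 268 evaluable (Section XIII). 1:1 allocation (Appendix A). Chi-square test (Section XII).

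**Step 1: range of the composite.**
- No overlap: 20 + 5 + 5 = 30%.
- Independence: 1 − 0.80 × 0.95 × 0.95 = 1 − 0.722 = 27.8%.
- Full overlap (all GC and syphilis cases also have CT): 20%.

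**Step 2: formula.** With p̄ = (p₁ + p₂)/2 and n per arm,

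power = Φ{ [ |p₁ − p₂| − c − 1.96 √(2p̄(1 − p̄)/n) ] / √( [p₁(1 − p₁) + p₂(1 − p₂)]/n ) },

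where c = 0 for the uncorrected chi-square and c = 1/n with continuity correction.

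**Step 3: reproduce the plan's figures.**
- Aim 2, 30% v 15%, n = 154: (0.150 − 0.0933)/0.0468 = 1.21, so power is 88.7% (85.8% corrected). The claim of more than 80% is reproduced on the plan's own inputs.
- Aim 1, 30% v 15%, 80% power: 121 per arm uncorrected and 134 per arm corrected. The plan states 134, so its Aim 1 figure matches the continuity-corrected method.

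**Step 4: power for p v p/2 (uncorrected / continuity-corrected).**

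| Control composite | 154 per arm (308) | 134 per arm (268) |
|---|---|---|
| 30% (no overlap) | 88.7% / 85.8% | 84.0% / 80.2% |
| 27.8% (independent) | 85.5% / 82.0% | 80.3% / 75.8% |
| 20% (full overlap) | 69.2% / 63.4% | 63.1% / 56.5% |
| Lowest composite keeping 80% power | 24.7% / 26.8% | 27.6% / 29.9% |

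Worked cell, 27.8% v 13.9%, n = 134: (0.139 − 0.0973)/0.0489 = 0.853, giving 80.3%. With c = 1/134 = 0.0075 the numerator falls to 0.0342 and power to 75.8%. Exact enumeration of the uncorrected test agrees within one percentage point (81.1% for this cell).

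**Step 5: the evaluable number.** 268/308 = 87.0%, which is 13% loss. Taking the full 15% from 308 leaves 261.8, about 131 per arm. Power there is 83.2% / 79.2% at 30% and 79.4% / 74.8% at 27.8%, so 268 is not a pessimistic choice.

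**The case against.** The case for leaving the sentence alone has real substance.

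- **The claim survives on its own number.** A reader might infer that the power claim depends on no woman having two infections. It does not. At 308, independence gives 85.5%, and even a composite of 25% gives 80.5% uncorrected. Overlap alone, from 30% to 27.8%, costs 3 to 4 points uncorrected and does not cross 80% at either sample size. The shortfall needs overlap together with the smaller evaluable number, or the continuity correction as well. This stands.
- **30% is attainable.** It would be wrong to say the components cannot produce it. They can, in the extreme case.
- **The effect size is not a second error.** Halving each infection independently gives 1 − 0.90 × 0.975 × 0.975 = 14.4%, which is 48% below 27.8%. A reader might call that a slip, but the plan halves the composite and nowhere says that each organism is halved.
- **The background rates point upward.** Section II cites a study in which "38% of pregnant women with HIV had CT (compared to 7% in HIV-uninfected), 10% had GC (compared to 3%) and 36% had syphilis". It is tempting to use this as proof of co-infection. The three rates sum to 84%, so they force none, and no co-infection rate is given. They imply a composite of at least 38%, and at 38% v 19% uncorrected power is 93.6% with 134 per arm. If the sponsor took the composite from there, 30% would be conservative. However, Section XI uses 20%, 5% and 5%, and its composite has to follow from those or be sourced separately.
- **Retention may be better than planned.** Section XIII aims for more than 95%. Power would then lie between the two columns of the table. Even so, 308 evaluable would require no loss at all.
- **Aim 1 sets the sample size.** Aim 2 power is a by-product, so no design decision turns on it. That limits the consequence but does not make the sentence correct.

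**Conclusion.** The point holds in a limited form. The expected composite is the upper bound of a 20–30% range, presented without that qualification, and 308 is labelled evaluable when the plan elsewhere expects 268.

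At 308 the claim of more than 80% survives independence under both conventions. At 268 it is borderline under independence: 80.3% uncorrected, 75.8% by the convention that matches Aim 1. It fails once the composite drops below about 27.6% uncorrected or 29.9% corrected, which any appreciable clustering would bring about. At full overlap it is 63.1% / 56.5%.

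The assumptions are a 50% reduction applied to the composite, equal arms and the stated component rates. Independence and full overlap are illustrative, because the documents give no co-infection rate. For the same reason no single intermediate value, such as 25%, can be put forward as the expected composite. The documents do not support saying that Aim 2 is underpowered, only that its stated margin is not secured.

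**What to change.** Rewrite the Aim 2 sentence in Section XI to:

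1. use 268 evaluable women, in agreement with Section XIII;
2. either cite a direct source for a 30% composite, or give 27.8% under independence with a range of 20–30%. A higher figure drawn from the Section II rates is open to the sponsor if it is justified and the component rates are changed to match;
3. name the test convention (with or without continuity correction) and use the same one for Aims 1 and 2;
4. replace the statement of more than 80% with power across the range: about 76–80% under independence at 268, with the values at 30% and 20% alongside.

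The cost is one sentence and a slightly less favourable stated power. Enrolment, endpoint and analysis do not change.
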